8.2. SECONDARY EVALUATION CRITERIA

The secondary evaluation criteria are:

[figure not shown]
- the socio-demographic characteristics: age, occupation;
- the characteristics of lymphedema: origin, date of onset, stage of edema according to the classification of the international society of lymphology, laterality of edema, volume of the arm with lymphedema, and volume of lymphedema compared to the contralateral arm;
- the PGII and CGII;
- the adherence of patients to the wearing of their maintenance treatment by the adapted Morisky score;
- the patient satisfaction in terms of efficiency and wearing comfort measured on Likert scales in 5 classes;
- the occurrence of adverse events and their imputability to the products under study according to the materiovigilance;
- the quality of life of the patients measured by the IFC Lymph specific questionnaire;
- the opinion of the person on the ease of use of the product during the maintenance phase: need of a third person, applications of pressure, continued use, advice to third parties, comparison with possible previous treatments, ease of use employment;
- the need of nurses or caregivers for the setting up of the decongestive device during the maintenance phase.

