13.1. SAMPLE SIZE

The sample size is based on the assumption that at the end of the maintenance period, 3 out of 4 patients will have at least a 20% decrease in the volume of their lymphedema in the circaid® group versus 1 in 2 in the control group. At risk alpha = 0.05, in a two-sided Chi2 test with a power of 80%, the calculation performed with Nquery (see table below) shows that the number of patients required to highlight this difference is 58 patients per group. This number is increased by 15% to account for patients lost to follow-up or unusable records, i.e. 68 per group. These patients will be recruited by 5 centers on the basis of 28 patients per center. Two group χ^2 test of equal proportions (odds ratio = 1) (equal n's)

Test significance level, α	0,050
1 or 2 sided test?	2
Group 1 proportion, π_1	0,250
Group 2 proportion, π_2	0,500
Odds ratio, $\psi = \pi_2 (1 - \pi_1) / [\pi_1 (1 - \pi_2)]$	3,000
Power (%)	80
n per group	58

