13.4.3. Studies of secondary objectives

- The evolution of the volume of lymphedema will be compared between the groups by repeated-time analysis of variance with two time factors and treatment with interaction on D5, DD + 30 and DD + 90.
- The frequency of patients whose lymphedema volume reduction is at least of 20% of the initial volume is described by numbers, frequencies, 95% confidence intervals and compared between groups by a Chi2 test at D5 and DD + 90.
- The percentage of patients for whom 70% of the initial benefit of the reduction of lymphedema obtained on day 5 is kept at DD + 90 at the end of the maintenance phase is described by number, frequency, 95% confidence interval and compared between groups by a Chi2 test at DD + 90.
- The improvement of the discomfort will be described through the CGII and the PGII (Patient Global Improvement Impression) by numbers, percentages and 95% confidence intervals and compared between groups by Wilcoxon rank tests. The evolutions within each group will be compared by Wilcoxon tests on repeated series.
- The improvement of the quality of life will be described through the IFC-specific Lymph Questionnaire by means of means, standard deviations and 95% confidence intervals and compared between the groups by a two-factor repeated time analysis of variance with interaction measurement. A Student's t-test will compare their variations between the two groups. The evolutions within each group will be compared by t-tests on repeated series.
- Their compliance with the Morisky score, the satisfaction of the patients in terms of efficiency and wearing comfort, their opinion on the ease of use of the product (need of a third person, applications of pressure, continuation of his use, advice to third parties, comparison with possible previous treatments, ease of use) will be compared between groups by Chi2 test or by a Fisher test if the characteristics of the distributions require it.
- The frequency and nature of adverse events will be described in terms of numbers and frequencies and compared between groups by Chi2 tests or Fisher tests if required by distribution conditions.
- The evolution of the quality of life of the patients will be described by numbers, percentages and 95% confidence interval and compared between groups by Wilcoxon rank tests. The evolutions within each group will be compared by Wilcoxon tests on repeated series.

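### Satisfaction and wearing comfort are 5-class ordered scales, but section 13.4.3 compares them with tests that ignore the order; a rank or proportional-odds test would be more efficient at no cost

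*Combined protocol and SAP*

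**What the plan says.** Section 8.2 lists, among the secondary criteria, "the patient satisfaction in terms of efficiency and wearing comfort measured on Likert scales in 5 classes" and "the adherence of patients to the wearing of their maintenance treatment by the adapted Morisky score". It gives no number of levels, cut-off or grouping for the adherence score.

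Section 13.4.3 takes adherence, satisfaction, wearing comfort and the ease-of-use opinions together and says that they "will be compared between groups by Chi2 test or by a Fisher test if the characteristics of the distributions require it". It names no trend version, class scores or grouping of classes. Earlier in the same section, the CGII and PGII are to be "compared between groups by Wilcoxon rank tests".

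The only sample-size or power figure is in section 13.1 and concerns the primary endpoint: "the number of patients required to highlight this difference is 58 patients per group". No expected distribution, effect or power target is given for satisfaction, comfort or adherence.

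**The concern.** A Pearson Chi2 on a 2 by 5 table has 4 degrees of freedom and returns the same p-value if the five class labels are shuffled. The Fisher test also ignores order. When one arm is rated consistently higher, an ordered test puts its power on one degree of freedom, whereas the unordered test spreads it over four.

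The plan already applies a rank test to similar ordered ratings in the same section and gives no reason for treating these two scales differently.

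Satisfaction and comfort are named secondary objectives (section 2.2), and section 1.2 presents comfort as one of the advantages of the device. At stake is the efficiency of these secondary comparisons, and the lack of a single directional summary of the difference. Neither bias nor the primary result is at stake.

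**Working it through.** **1. Inputs from the documents.** Five ordered classes (section 8.2); two-sided alpha of 0.05 and 58 evaluable patients per arm (section 13.1).

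**2. The plan's own figure.** Section 13.1 states "At risk alpha = 0.05, in a two-sided Chi2 test with a power of 80"%, with 3 in 4 against 1 in 2 responding. With mean proportion 0.625:

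n = [1.96·√(2·0.625·0.375) + 0.8416·√(0.75·0.25 + 0.5·0.5)]² / 0.25² = (1.3419 + 0.5567)² / 0.0625 = 57.7, so 58 per group.

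The figure reproduces. The 25% v 50% in the software table is the mirror image and gives the same n.

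**3. Assumptions for the comparison.** The documents give no distribution or effect for these scales, so both are assumed. Three control distributions over the five classes were used: (10, 20, 30, 25, 15)%, (5, 10, 25, 35, 25)% and (20, 20, 20, 20, 20)%. The other arm has every cumulative odds divided by a common odds ratio (OR). Example: the uniform control has cumulative odds 0.25, 0.667, 1.5 and 4. Dividing by OR 2 gives 0.125, 0.333, 0.75 and 2, hence classes of 11.1, 13.9, 17.9, 23.8 and 33.3%.

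**4. Tests.**
- Chi2: X² = Σ(O − E)²/E on 4 df.
- Wilcoxon: z = [W − n(M+1)/2] / √{(n²/12)·[(M+1) − Σ(t³ − t)/(M(M−1))]}, where M = 2n = 116, W is the rank sum in one arm and t is the number of patients in each class.

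**5. Simulated power**, 58 per arm, 40,000 trials per setting, range over the three distributions:

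| OR | Wilcoxon | Chi2 | Loss (points) |
|---|---|---|---|
| 1 (type I error) | 5% | 5% | 0 |
| 1.5 | 22–23% | 12–14% | 10 |
| 2 | 53–55% | 32–34% | 21 |
| 2.5 | 76–79% | 54–57% | 22–23 |
| 3 | 89–90% | 71–74% | 16–18 |
| 4 | 98–99% | 90–92% | 6.3–7.5 |

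With a further set of five assumed shapes, including more skewed ones, the losses at 58 per arm are 9–10 points at OR 1.5, 21–22 at OR 2, 21–23 at OR 2.5, 17–20 at OR 3 and 6–10 at OR 4. At 68 to 70 per arm they are 11–12 at OR 1.5, 19–22 at OR 2.5, 12–16 at OR 3 and 3–6 at OR 4.

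**6. Cross-check without simulation.** For equal noncentrality λ, compare the noncentral chi-square on 1 df (critical value 3.84) with that on 4 df (9.49). For 80% power on 1 df, λ = 7.85, and the 4-df power is 60%. For 1-df power of 50, 60, 70, 80 and 90%, the 4-df power is 31, 39, 48, 60 and 74%, a loss of 19, 21, 22, 20 to 21 and 16 points.

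**7. Where the advantage disappears.**
- Not a shift: control (5, 10, 20, 40, 25)% against (5, 10, 20, 20, 45)% gives Wilcoxon about 25% and Chi2 56%.
- Three ordered levels: the loss is 7–10 points for OR 1.75 to 3.
- Two levels: the loss is zero, because the two tests coincide.

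**The case against.** **The plan may intend to group the classes.** Section 13.4.3 ends by studying the factors behind adherence and satisfaction with logistic regression, and no ordinal version is named. If the scales are dichotomised first, Chi2 or Fisher is a suitable test. This stands as a possibility, but no cut-point appears anywhere. A split has its own cost: with half the controls above the cut, Chi2 power at 58 per arm is 44, 66 and 80% at OR 2, 2.5 and 3, about 9 to 13 points below the Wilcoxon figures for the full scale. An unstated cut in an open-label trial can also be chosen after the data are seen. On either reading the sentence needs completing.

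**Details are deferred.** Section 13.2 promises a later, detailed analysis plan that will name the tests. The choice is therefore not shown to be final. But that plan is to rest mainly on section 13, so the unordered test carries forward unless someone changes it.

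**The power loss is conditional.** This stands in full. A reader might infer a fixed cost of roughly 15 to 22 points. The documents give no effect or distribution for these scales, and over the assumed settings the loss runs from about 3 to 23 points. Proportional odds is also a pattern that favours Wilcoxon.

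**A real benefit is not necessarily lost.** A reader might infer that Chi2 would probably miss a true shift. At OR 2.5 and 3 its power is above 50%, so detection is more likely than not. At OR 2 a miss is likely with Chi2, but Wilcoxon is then only slightly better than even.

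**Direction is not hidden.** It can be read from the class frequencies. What Chi2 lacks is a directional summary with a confidence interval.

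**Conclusion.** The point holds for the two 5-class scales, satisfaction with efficiency and wearing comfort. The planned tests ignore the order of the classes, and the section is inconsistent with its own handling of the CGII and PGII. The planned analysis is valid but inefficient: about 16 to 23 points of power lost at 58 per arm, assuming a proportional-odds shift of OR 2 to 3. The loss is about 10 points at OR 1.5 and about 7 at OR 4, and the ranking can reverse when the difference is not a shift.

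A reader might extend the same loss to the adherence score. The documents do not support that: the levels of the adapted Morisky score are not stated, and the loss would be nil if it is dichotomised and 7 to 10 points with three levels. No loss is claimed for it. Nor is any claimed for the ease-of-use items, whose response formats are not given.

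These are secondary outcomes with no power target, and the primary analysis is unaffected. This is a worthwhile improvement, not a flaw that threatens the trial's conclusions.

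**What to change.** In section 13.4.3, and in the detailed analysis plan that follows from it:

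- Compare the two 5-class scales between arms by the Wilcoxon rank-sum test, or by proportional-odds regression reporting a common odds ratio with a 95% confidence interval. The regression also supplies the directional summary.
- State the levels and handling of the adapted Morisky score. If it is analysed with three or more ordered levels, use the same test.
- If any grouping of classes is intended, fix the cut-point before the data are seen.
- State the response format of each ease-of-use item, and keep Chi2 or Fisher for those that are binary.

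The cost is a few lines of text. No extra data, visits or patients are needed.

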- collects the quality of life measured by the Lymph IFC specific questionnaire;
- gives the patient a self-questionnaire on which she reports each week who has placed the contention device (herself, spouse, nurse), and the existence of an intolerance to the wearing of it;
- gives the patient, according to the randomization list, the products under study during the maintenance phase;
- provides a nursing prescription for the application of a possible treatment to the patients concerned.

At DD + 30 days (+/- 5 days), the doctor:

- collects the characteristics of lymphedema: stage of edema according to the classification of the international society of lymphology, volume of the arm with lymphedema, and volume of lymphedema compared to the contralateral arm;
- collects the PGII and CGII;
- collects the quality of life measured by the Lymph IFC specific questionnaire;
- records patient satisfaction in terms of efficiency and wearing comfort measured on Likert scales in 5 classes;
- collects the observance of the port during the initial maintenance phase by the adapted Morisky score;
- collects the occurrence of adverse events and their imputability to the products under study according to the materiovigilance;
- retrieves the self-questionnaire from the early maintenance period and gives the patient a self-questionnaire for the maintenance period where she reports on each week who apply the compression device (herself, spouse, nurse), and the existence of an intolerance to the wearing of it;
- provides a nursing prescription for the application of a possible treatment to the patients concerned;
- gives the patient, according to the randomization list, the products under study during the maintenance phase.

At DD + 90 days (+/- 10 days), the doctor:

- collects the characteristics of lymphedema: stage of edema according to the classification of the international society of lymphology, volume of the arm with lymphedema, and volume of lymphedema compared to the contralateral arm;
- collects the PGII and CGII;
- collects the quality of life measured by the Lymph IFC specific questionnaire;

- records patient satisfaction in terms of efficiency and wearing comfort measured on Likert scales in 5 classes;
- collects the observance of the port during the long-term maintenance phase by the adapted Morisky score;
- collects the occurrence of adverse events and their imputability to the products under study according to the materiovigilance;

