13.4.5. Analysis software

Data record will be done on capture system and the analyzes will be conducted using the SAS software version 9.4. The significance level is set to $\alpha = 0.05$.

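### Section 13.4.3 gives the single quality-of-life questionnaire two different, unranked between-arm analyses and names no visit for the t-test or the Wilcoxon test

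*Combined protocol and SAP*

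**What the plan says.** Section 8.2 lists one quality-of-life measure: "the quality of life of the patients measured by the IFC Lymph specific questionnaire". Section 9 collects it at D0, D5, DD+30 and DD+90, each time with the same instruction ("collects the quality of life measured by the Lymph IFC specific questionnaire").

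Section 13.4.3 then has two separate bullets.

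- **Fifth bullet.** "The improvement of the quality of life will be described through the IFC-specific Lymph Questionnaire by means of means, standard deviations and 95% confidence intervals", with the score "compared between the groups by a two-factor repeated time analysis of variance with interaction measurement". It adds a second between-arm test: "A Student's t-test will compare their variations between the two groups". Changes within each arm are tested by paired t-tests.
- **Eighth bullet.** "The evolution of the quality of life of the patients will be described by numbers, percentages"; the full specification is "numbers, percentages and 95% confidence interval and compared between groups by Wilcoxon rank tests". Changes within each arm are tested by Wilcoxon tests. No instrument is named.

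Section 13.4.5 adds "The significance level is set to" 0.05 for the analyses in general. No multiplicity rule appears. Section 13.2 says that a detailed analysis plan, based mainly on this part of the protocol, will be written later and will identify the tests.

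**The concern.** Two bullets prescribe different summaries, different between-arm tests and different within-arm tests for one questionnaire, and the plan does not say which gives the quality-of-life result. Counts and percentages also do not suit a score that the plan itself summarises by means and standard deviations.

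The trial is open label (section 4), an interim analysis may be run once half the patients have completed (section 13.4.4), and the detailed plan has still to be written. If the choice stays open, whichever test favours the device could be the one reported. Section 1.2 presents better quality of life as an advantage of the device and says the study is meant to support reimbursement in France. A quality-of-life statement is therefore likely to be read with interest, even though it is secondary.

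**Working it through.** **1. Do both bullets concern the same data?** The eighth bullet names no instrument, but sections 8.2 and 9 contain only the one questionnaire. It can refer to nothing else that is collected.

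**2. Is one analysis a fallback for the other?** The plan writes fallbacks where it wants them. Section 13.4.1 allows non-parametric equivalents, but only for baseline comparability. Several bullets of section 13.4.3 and its continuation allow Fisher in place of chi-square. Neither quality-of-life bullet has such a condition.

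**3. Which visit and which scale?** The volume and responder bullets of section 13.4.3 name their visits. The quality-of-life bullets name none. The t-test is on changes. The Wilcoxon test could be on changes or on raw scores.

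**4. Number per arm.** The plan gives no figure for quality of life, so I used the 58 per group of section 13.1, which reproduces:

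n = [1.960·√(2·0.375·0.625) + 0.842·√(0.25·0.75 + 0.5·0.5)]² / 0.25² = (1.342 + 0.557)² / 0.0625 ≈ 57.7, so 58, with power 80.2%.

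**5. Error rate if any of the tests may be chosen.** Reference for independent tests at 0.05: 1 − 0.95² = 9.75% for two and 1 − 0.95³ = 14.3% for three. These tests are correlated, so the rate was simulated with no true effect. Assumptions that are not in the documents: normal scores at D0 and three later visits, equal correlation between visits of 0.5 or 0.7, complete data, 4,000 trials per setting.

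| Tests counted (at least one p<0.05) | corr. 0.5 | corr. 0.7 |
|---|---|---|
| DD+30: t-test or Wilcoxon, both on change | 7.0% | 5.9% |
| DD+30: the same plus ANOVA interaction | 9.8% | 9.0% |
| DD+30: interaction, t-test on change, Wilcoxon on raw score | 12.4% | 11.7% |
| All three visits: interaction, t-tests and Wilcoxon on change | 17.7% | 15.6% |
| All three visits: the same, Wilcoxon on raw score | 24.0% | 21.5% |

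The Monte Carlo standard error is about √(0.07·0.93/4000) = 0.4 points in the first row and √(0.24·0.76/4000) = 0.7 points in the last.

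A separate run of 8,000 trials per setting, at DD+90, with correlations 0.3, 0.5 and 0.7 and one skewed case at 0.5, agrees: 5.7-6.6% for t-test or Wilcoxon on change, and 8.5-9.5% with the interaction.

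**6. Where the inflation comes from.** Against a single test at 5%, adding Wilcoxon on the same changes costs about 1 to 2 points. Going from DD+30 alone to three visits adds 17.7 − 9.8 = 7.9 and 15.6 − 9.0 = 6.6 points with Wilcoxon on change, or 24.0 − 12.4 = 11.6 and 21.5 − 11.7 = 9.8 with Wilcoxon on raw score. In the 8,000-trial run, the interaction with t-tests at all three visits, and no Wilcoxon test at all, already gives 13.3% and 13.4% at correlations 0.5 and 0.7.

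**The case against.** - **The later plan will settle it.** Section 13.2 does assign the identification of tests to a later document, which could resolve the point. It is to be based mainly on a section that contradicts itself, and nothing says it will be final before data are seen. This softens the concern but does not remove it.
- **It is a drafting slip.** The eighth bullet nearly repeats the CGII/PGII bullet, so a carry-over is plausible. The documents do not confirm it. If it is one, that is a reason to delete the bullet.
- **The tests usually agree.** This stands. A reader might infer that the plan must give contradictory quality-of-life results. It does not: a t-test and a Wilcoxon test on the same changes are highly correlated. They can disagree; nothing shows that they will.
- **The duplicate bullet does not cause a 20% error rate.** This stands too. A reader might attribute the all-visit figures to the duplication, but much of them comes from the unstated visit and would remain if the bullet were deleted and every visit still tested.
- **The stakes are low.** Quality of life is a secondary criterion in section 8.2 and is absent from the objectives in section 2.2. No confirmatory claim is planned, and no secondary endpoint has multiplicity control. This limits the weight of the point.
- **A new model is not needed to remove a duplicate.** True. Ranking the existing analyses and naming a visit would be the minimum. Adjustment for the D0 score is a recommendation that uses data already collected.

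**Conclusion.** The conflict is real and stated in the text: one questionnaire, two unranked sets of analyses, and no visit for the t-test or the Wilcoxon test. It should be corrected before the analysis plan is finalised.

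Its size is modest. With free choice at DD+30, the chance of a nominally significant result under no effect is about 6-7% for t-test or Wilcoxon on change, 9-10% with the interaction, and about 12% if Wilcoxon is applied to raw scores. It reaches about 16-24% only if all three post-baseline visits are also open to choice. These figures rest on the assumed 58 per arm, normal scores and correlation of 0.5 to 0.7.

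The documents do not support reading this as a threat to the trial's main conclusion: the primary chi-square test at DD+30 (section 13.4.2) and the sample size (section 13.1) do not depend on it. Nor do they show that any selection is intended.

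**What to change.** In section 13.4.3, and in the detailed analysis plan:

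1. Delete the second quality-of-life bullet and the separate t-test on changes.
2. Keep one longitudinal model of the questionnaire score at D5, DD+30 and DD+90, with treatment, visit, treatment-by-visit and the D0 score as covariate.
3. Name one visit contrast, with its 95% CI, as the quality-of-life result. DD+30 would match the primary time point; the documents do not set a visit for quality of life.
4. Label any rank test as a sensitivity analysis, and state its visit and whether it uses change or raw score.

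The cost is wording only: no new data, visits or patients. The small downside is giving up the alternative p-values.

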- The frequency of those who use nurses or caregivers will be described by numbers, percentages, and 95% confidence intervals and will be compared between groups by Chi2 tests or Fisher tests if the characteristics of the distributions required it. The average number of nurse visits and its standard deviation will be calculated and compared between groups by Student's t tests. Its economic impact will be quantified by mean and standard deviation and compared by Student t tests on repeated series.
- The sociodemographic and clinical factors of patients likely to influence their adhesion, their satisfaction and the maintenance of the effect on lymphedema will be studied by logistic regression analyzes in order to identify those having a significant action after adjustments on the socio-demographic and clinics characteristic of the patients.

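### Factors for maintenance of the volume effect are sought by logistic regression alone, which cuts a measured volume to yes/no and can cost power, by an amount that depends on how the factor acts

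*Combined protocol and SAP*

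**What the plan says.** The last item of section 13.4.3 names one method for finding the sociodemographic and clinical factors behind three outcomes: adhesion, satisfaction and volume maintenance. On the third it reads: "the maintenance of the effect on lymphedema will be studied by logistic regression analyzes in order to identify those having a significant action". The models adjust for patient characteristics. The item does not say which variable represents maintenance.

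The closest definition is an earlier item of the same section: "The percentage of patients for whom 70% of the initial benefit of the reduction of lymphedema obtained on day 5 is kept at DD + 90". That item specifies a between-group Chi2 test, and no expected rate is given.

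Section 8.1 computes arm volumes from perimeters taken every 5 cm and defines lymphedema volume as the affected arm minus the healthy arm. Section 9 has the doctor record, at D0, D5, DD+30 and DD+90, "volume of the arm with lymphedema, and volume of lymphedema compared to the contralateral arm". Volume is analysed as continuous once, in the repeated-measures analysis of variance of section 13.4.3, whose factors are time and treatment only. Section 13.2 says that a detailed analysis plan is still to be written.

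**The concern.** Logistic regression needs a categorical outcome, so the volumes must be cut before any factor can be tested. A patient who just misses the cut then counts the same as one who has lost the whole benefit. The plan gives no reason for doing this in a search whose stated purpose is to find significant factors, and no continuous model offsets it.

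Two features of the likely outcome add to this. A ratio to the D5 benefit is undefined for a patient with no reduction at D5 and unstable for one with a small reduction. And if most patients keep the effect, the model rests on few patients who do not.

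At stake is a secondary result: a characteristic that matters for maintenance could go undetected although the recorded volumes would have shown it.

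**Working it through.** **1. The plan's own figure.** Section 13.1 assumes that "3 out of 4 patients will have at least a 20% decrease in the volume of their lymphedema in the circaid® group" (0.75), against one half of the controls (0.50), with two-sided alpha 0.05 and 80% power. The formula is n = [1.96·√(2p̄(1−p̄)) + 0.842·√(p1(1−p1)+p2(1−p2))]² / (p1−p2)², with p̄ = 0.625.

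- 1.96 × √0.46875 = 1.342, and 0.842 × √0.4375 = 0.557.
- n = (1.899)² / 0.0625 = 57.7, so 58. This agrees with the statement that "the number of patients required to highlight this difference is 58 patients per group".
- The 15% allowance gives 58/0.85 = 68.2, stated as 68 per group.

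So 116 evaluable patients and success rates of 50-75% are the plan's only usable inputs. Those rates belong to the 20%-reduction criterion, not to maintenance. Effect size, factor prevalence and maintenance rate below are assumptions.

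**2. Cost of the cut, by formula.** Assume a normal outcome and a factor present in half of N = 116. A linear analysis has power P when the standardised effect is d = (1.96 + z_P) × 2/√116. This gives d = 0.520 for 80% and 0.602 for 90%. Cut the outcome so that a share s succeed. The success rates with and without the factor are Φ(d−c) and Φ(−c), with c chosen so that they average s. These two rates are then compared by the two-proportion test with 58 per level.

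Example: P = 80%, s = 50%, c = 0.26. The rates are 0.603 and 0.397, a difference of 0.205. Power = Φ[(0.205 − 1.96·√(0.5/58)) / √(0.479/58)] = Φ(0.26) = 60%.

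| Share keeping the effect | Power after cut, from 80% | Loss | Power after cut, from 90% | Loss |
|---|---|---|---|---|
| 50% | 60% | 20 | 73% | 17 |
| 62.5% | 58% | 22 | 71% | 19 |
| 75% | 52% | 28 | 64% | 26 |
| 85% | 42% | 38 | 52% | 38 |
| 90% | 34% | 46 | 43% | 47 |

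With N = 136 each loss changes by less than one point.

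**3. The same by simulation with covariates.** n = 116, a factor present in 40%, four other covariates including arm, normal residuals, 1,500 runs per cell. Entries are linear v logistic power.

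| Odds ratio on the cut outcome | 50% keep | 62.5% | 75% | 85% |
|---|---|---|---|---|
| 2 | 53 v 36 | 54 v 36 | 56 v 32 | 55 v 21 |
| 2.5 | 80 v 58 | 78 v 54 | 78 v 46 | 78 v 32 |
| 3 | 91 v 75 | 91 v 70 | 91 v 59 | 92 v 45 |

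The losses are 16 to 32 points at 50-75% and 34 to 47 at 85%.

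**4. A model close to the fix.** Log DD+90 volume was regressed on log D5 volume, arm and factor, and compared with logistic regression of the 70%-kept criterion (n = 116, shift effect). Power was 51-54% v 32-38%, 78-82% v 50-57% and 94-95% v 74-78%, a loss of about 16 to 28 points. Log D0 volume was not in that model.

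**5. Where the range does not apply.**

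- *Weak factor:* at a standardised effect of 0.2 (balanced, N = 116), the loss is 5 points at 50% and 7 at 75%, because both analyses are weak (19% v 13% and 19% v 12%).
- *Strong factor:* at 0.8, the loss is 6 points at 50% and 13 at 75%.
- *Uncommon factor:* present in 20% of patients, with 75% keeping the effect and linear power of 80-90%, it loses about 42 points.
- *Factor acting on relapse:* assume 38% relapse, with skewed regain among them and an odds ratio of 2.5-3. In one version logistic regression was level or better (46% v 37% and 61% v 51% with residual SD 0.2; 37% v 35% and 51% v 48% with SD 0.3). In another, linear regression was level or slightly better.

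**6. Sparse events.** Sections 9 and 13.4.1 list eight characteristics: age, occupation, origin, onset date, stage, laterality, arm volume and lymphedema volume. If 75% keep the effect, 0.25 × 116 = 29 patients do not, which is 29/8 = 3.6 per characteristic. At 85% it is about 17, or 2.1 each. Multi-category items lower this further.

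**The case against.** The cut may be deliberate. The plan uses responder definitions for its main criterion and for maintenance at DD+90, and a logistic model of who keeps 70% of the benefit is coherent with that endpoint. This stands as a reason to keep the logistic model. It does not show that it should be the only one, since the 70% criterion is specified for a group comparison and is not named as the regression outcome.

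The linear model's advantage also rests on assuming that a factor shifts volume. The Introduction describes loss of effect as reappearance, in 38.1% of women in a cited cohort, and a factor acting mainly on relapse would gain little or nothing from a linear model. This stands, and the size must be stated with that condition.

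A reader might infer that the plan as written loses 17 to 47 points of power. The documents do not support an unconditional figure: they give none of the inputs, and the upper end needs 85-90% of patients to keep the effect. A reader might also infer that the trial would report that no characteristic affects maintenance. The plan nowhere says that it will read non-significance that way. Nor does the point reach the main comparison. The factor search is not among the objectives in section 2.2, carries no power claim, and leaves the between-group volume analysis continuous.

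**Conclusion.** The point holds in a conditional form. For maintenance of the effect, the only planned factor analysis discards measured information, and the modelled outcome is not defined.

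The loss is roughly 16-30 points (single simulated cells reach 32) under four assumptions: 116 evaluable patients, a factor present in about 40-50% of them, an effect that shifts volume enough to give a linear model about 50-90% power, and 50-75% of patients keeping the effect. It rises to about 47 points if 85-90% keep it. It is smaller for very weak or very strong factors, larger for uncommon ones when most patients keep the effect, and little or none if the factor works through relapse. The calculations assume normal residuals, and skewed volumes would change them.

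This is a low-priority improvement to an unpowered secondary analysis. Adhesion and satisfaction are not volume measurements and are not affected. The primary analysis is unaffected.

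**What to change.** In section 13.4.3 and the detailed analysis plan, for maintenance only:

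- Make the main factor analysis a linear regression of log lymphedema volume at DD+90 on the patient factors, with log D5 volume, log D0 volume and treatment arm as covariates.
- If any lymphedema volume is zero or negative, model affected-arm volume with contralateral volume as a covariate.
- Report the adjusted percentage difference in volume for each factor with its 95% confidence interval.
- Keep a logistic model as a named companion, and state that its outcome is the 70%-of-D5-benefit criterion at DD+90.

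D5 volume is measured after randomisation, so the arm coefficient in this model should not be reported as the treatment effect.

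The cost is wording only: all the volumes are already collected, and no visit or patient is added. The downside is that results read as percentage differences in volume instead of odds ratios, and residuals need a routine check.
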